## 7.5.6 Vital Signs

Vital signs data will be presented descriptively for each visit (refer to Table 7-7 and Table 7-8 for analysis visit window definition) and separated by predose and post-infusion (refer to Section 7.1.4.3 for handling of predose and post-infusion) per each visit; the actual values and CFB will be summarized. Selection of data in the event of multiple records in an analysis visit window is specified in Section 7.1.3.2, separately for measurement time point (predose, post-infusion, and not applicable).

A post-baseline vital signs value is considered treatment-emergent potentially clinically significant (PCS) if it meets both the observed value and the CFB criteria as listed in Table 7-24 during the treatment period. The number and percentage of participants with post-baseline treatment-emergent PCS vital signs will be summarized for each post-baseline visit and overall during the treatment period. The summary will be separated by measurement time point (predose, post-infusion, and not applicable) per visit or overall. For overall, the record with the most severe finding will be selected for a participant, separated by measurement time point (predose, post-infusion, and not applicable). Vital signs with measurement time point missing will only be included in the by-participant data listing.

All vital signs will be listed.

Table 7-24. Criteria for PCS Vital Signs

		Criteria a	
Parameter	Flag	Observed Value	CFB
Suming exertable blood masses (man He)	High	≥ 180	Increase of ≥ 20
Supine systolic blood pressure (mmHg)	Low	≤ 90	Decrease of $\geq 20$
Symina diastalia bla ad mussayus (mm.Ha)	High	≥ 105	Increase of $\geq 15$
Supine diastolic blood pressure (mmHg)	Low	≤ 50	Decrease of $\geq 15$
Suming mulas meta (hanta/min)	High	≥ 120	Increase of $\geq 15$
Supine pulse rate (beats/min)	Low	≤ 50	Decrease of $\geq 15$
Waight (Ira)	High	_	Increase of $\geq 7\%$
Weight (kg)	Low	_	Decrease of ≥ 7%

A post-baseline value is considered potentially clinically significant if it meets both the observed value and the CFB criteria.

## 7.5.7 Magnetic Resonance Imaging (MRI) for Detection of ARIA-E and ARIA-H

Incidence of the first occurrence of ARIA-E within each post-baseline visit will be summarized by radiographic severity for each visit (refer to Table 7-9 for analysis visit window definition) and overall during the treatment period. The same incidence table will be summarized for post-baseline new ARIA-H. In addition to radiographic severity for ARIA-H, individual radiographic severity for microhemorrhages, leptomeningeal hemosiderosis, and macrohemorrhages for the first occurrence of new ARIA-H will also be summarized by visit and overall during the treatment period.

Incidence of any occurrence of ARIA-E within each post-baseline visit will be summarized in the same fashion. In the case of multiple values in the baseline analysis visit window, the rules described in the Section 7.1.3.2 still apply. In the case of multiple values in a post-baseline analysis visit window, the

Protocol No. AL002-2 Last Revision Date: 12 Aug 2025

rules described in the Section 7.1.3.2 do not apply to this summary, but the worst-case scenario will be applied as below:

- A participant having a record indicating no ARIA-E and a different record indicating ARIA-E is considered experienced ARIA-E per visit or overall.
- A participant having experienced ARIA-E more than once per visit or overall is counted once in the number of participants with ARIA-E per visit or overall.
- The maximum severity is selected if ARIA-E was observed more than once for a participant per visit or overall post-baseline.

The same incidence table will be summarized for post-baseline new ARIA-H. In the case of multiple values in an analysis visit window, the same rules described above apply. In addition to radiographic severity for ARIA-H, individual radiographic severity for microhemorrhages, leptomeningeal hemosiderosis, and macrohemorrhages for the any occurrence of new ARIA-H will also be summarized by visit and overall during the treatment period. The maximum severity of ARIA-H is selected for a participant per visit or overall post-baseline, and the individual radiographic severity corresponding to the selected ARIA-H will be summarized per visit or overall post-baseline.

APOE genotype, time to the first occurrence, resolution, time to resolution, and reoccurrence will be summarized for participants with ARIA-E. APOE genotype and time to the first occurrence will be summarized for participants with post-baseline new ARIA-H.

The number and percentage of participants who had a post-baseline ARIA-E but did not have a new ARIA-H any time post-baseline will be summarized. The number and percentage of participants who had a new ARIA-H but did not have an ARIA-E any time post-baseline will be summarized. Similarly, the number and percentage of participants who had a new ARIA-H and an ARIA-E any time post-baseline will be summarized.

All the MRI summaries described above will also be provided separately for participants with the following APOE genotype(s) (1) e4/e4, (2) e4 carriers (including e2/e4, e3/e4 and e4/e4), (3) non-e4 carriers (excluding e2/e4, e3/e4 and e4/e4), and (4) e4 heterozygous carriers (including e2/e4 and e3/e4).

The Kaplan-Meier curve for the time to the first occurrence of ARIA-E will be plotted. For participants experienced at least one ARIA-E, the time to the first occurrence of ARIA-E is the time from the first dose date to the onset date of the first ARIA-E occurrence. For participants who did not experience ARIA-E, the censor date will be the earlier date of the last MRI scan date and the last dose date plus 90 days. Similarly, the Kaplan-Meier curve for the time to the first occurrence of new ARIA-H will be plotted.

All MRI findings will be listed.

Protocol No. AL002-2 Last Revision Date: 12 Aug 2025

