7.2. Adverse Events of Special Interest

An AESI is a serious or nonserious AE which is of scientific and medical concern specific to a product for which ongoing monitoring and rapid reporting by the Investigator to the Sponsor should occur. AESI for study AL002-2 are defined as the following occurrences:

- ARIA-H
 - There are 3 categories of ARIA-H which are considered separate AESI. See
 Section 7.11 for additional details.
- ARIA-E
- Uveitis Grade 2 or higher

For AESI, the most appropriate diagnosis should be recorded on the AE eCRF and reported to the Sponsor immediately (ie, no more than 24 hours after learning of the event) as an AESI, regardless of whether the AESI is deemed to have a possible relationship to the study drug or not.

Management of ARIA is described in Section 7.11.

Uveitis (Grade 2 or higher) should be managed by an ophthalmologist and the Medical Monitor.

The reporting of an AESI will trigger an auto notification email alert from EDC to the Medical Monitor.

In the event that EDC is not functioning, the Investigator should utilize the back-up paper process described below for SAE reporting and clearly indicate if the event is nonserious or serious, and related or not related to study drug in the opinion of the Investigator, and that the event is assessed as an AESI.

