To maintain consistency of reporting across clinical sites, findings of ARIA-E or ARIA-H on MRI are determined by the MRI Central Reader by radiologists with expertise in assessing for ARIA and other abnormalities on brain MRI. ARIA-E, ARIA-H and other findings are documented on and reported to the sites with the BMW report (see Section 6.5.12). The BMW provided by the Central Reader after each MRI examination scores ARIA-E (parenchymal vasogenic edema, leptomeningeal/sulcal effusion) according to: extent, location, number of sites involved, radiographic severity (mild, mild+, moderate, moderate+, severe) (Table 6) and changes since prior MRI exams. ARIA-E findings typically resolve radiographically and will be noted as such on the BMW of follow-up MRI scans. The BMW also documents occurrence and characteristics (location, size, number) of ARIA-H (parenchymal microhemorrhages and leptomeningeal hemosiderosis and macrohemorrhages).

Overall, ARIA-H radiographic severity is defined as the worst individual radiographic severity for microhemorrhages, leptomeningeal hemosiderosis or macrohemorrhages (eg, if there are

Alector, Inc.

4 incident microhemorrhages, 1 incident areas of leptomeningeal hemosiderosis and no macrohemorrhages, then ARIA-H is rated as "Moderate") (Table 6).

Table 6: ARIA-E and ARIA-H Radiographic Severity Scales

ARIA-E Characterization:		Severity/Grade	
<5 cm monofocal		Mild (Grade 1)	
<5 cm multifocal		Mild+ (Grade 2)	
5-10 cm monofocal	N	Moderate (Grade 3)
5-10 cm multifocal	Moderate+ (Grade 4)		
>10 cm monofocal/multifocal	Severe (Grade 5)		
Incident ARIA-H:	Mild	Moderate	Severe
microhemorrhages	1-4	5-9	10 or more
Areas of leptomeningeal hemosiderosis	NA	1	2 or more
macrohemorrhages	NA	NA	1 or more

ARIA-E=amyloid-related imaging abnormalities-edema; ARIA-H=amyloid-related imaging abnormalities-hemosiderin deposits; NA=not applicable.

ARIA-H findings very rarely resolve radiographically; it is more typical for ARIA-H findings to stabilize radiographically. Radiographic stabilization of an ARIA-H finding is defined as when a follow-up MRI scan shows no increase in number/size/extent of previously seen cerebral microhemorrhages, leptomeningeal hemosiderosis and cerebral macrohemorrhages.

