#### 6.3.7.2 New ARIA-H

#### 6.3.7.2.1 Event Definition

A new event of ARIA-H is defined as an MRI scan at a post-baseline visit if any of the criteria below as captured on its BMW is satisfied:

- CFB in the number of microhemorrhages > 0, or
- CFB in the number of areas of leptomeningeal hemosiderosis (also referred to as superficial siderosis) > 0, or
- Presence of macrohemorrhages.

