#### 6.3.7.2.2 Severity Definition

Individual radiographic severity for microhemorrhages, leptomeningeal hemosiderosis and macrohemorrhages is defined in Table 6-4. ARIA-H radiographic severity is defined as the worst individual radiographic severity among microhemorrhages, leptomeningeal hemosiderosis and macrohemorrhages for an MRI scan as captured in its BMW. If any macrohemorrhages are present at an MRI scan, then the ARIA-H radiographic severity is severe. If macrohemorrhages are absent at an MRI scan, then the worse severity between microhemorrhages and leptomeningeal hemosiderosis will be the ARIA-H radiographic severity. For example, if there are 4 incident microhemorrhages, 1 incident areas of leptomeningeal hemosiderosis and no presence of macrohemorrhages on a BMW, ARIA-H is rated as "Moderate".

Table 6-4. Definition for Individual Radiographic Severity related to ARIA-H

Incident (CFB) Findings	Mild	Moderate	Severe
Number of microhemorrhages	1-4	5-9	10 or more
Areas of leptomeningeal hemosiderosis		1	2 or more
Presence of macrohemorrhages	_	_	Yes

Protocol No. AL002-2 Last Revision Date: 12 Aug 2025

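### SAP 7.5.7: in the any-occurrence ARIA-H table, component severities come from the one selected ARIA-H scan with no tie-break, so a component on an equally graded scan can be missed or under-graded.

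*SAP*

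**What the plan says.** SAP 6.3.7.2.1 makes the scan the unit of the event: "A new event of ARIA-H is defined as an MRI scan at a post-baseline visit" meeting one of three component criteria. SAP 6.3.7.2.2 grades that scan: "ARIA-H radiographic severity is defined as the worst individual radiographic severity among microhemorrhages, leptomeningeal hemosiderosis and macrohemorrhages for an MRI scan". Table 6-4 gives the component grades.

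SAP 7.5.7 then has two sets of ARIA-H component summaries. The first reports component severity "for the first occurrence of new ARIA-H will also be summarized by visit and overall during the treatment period". The second covers any occurrence. It starts from the overall grade: "The maximum severity of ARIA-H is selected for a participant per visit or overall post-baseline". The component rows are then tied to that choice, since "the individual radiographic severity corresponding to the selected ARIA-H will be summarized per visit or overall post-baseline". For this second set the section switches off the usual record-selection rules of SAP 7.1.3.2 for post-baseline windows and announces a worst-case approach instead. That approach is spelled out for ARIA-E and carried over to ARIA-H. It covers presence and maximum overall severity, and says nothing about choosing between scans of equal overall severity.

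Protocol 7.2 says of the AESI definition: "There are 3 categories of ARIA-H which are considered separate AESI". Protocol 7.11 notes that "ARIA-H findings very rarely resolve radiographically".

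**The concern.** A grade defined as the worst of three components says nothing about the other two. Once a participant has reached a given overall grade through one component, a second component can appear or worsen without moving that grade. The participant then has two or more scans tied at the maximum, and the component rows depend on which one the programmer picks. Two programmers could produce different tables from the same data and both comply with the SAP.

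ARIA-H is an identified risk of AL002 (Protocol 1.3), and the protocol tracks its three types separately. These are the only planned tables of radiographic severity by type across all occurrences. The AESI tables are by system organ class and preferred term and do not use the Table 6-4 grades. The MRI summaries are also repeated for four APOE genotype groups, and in a small group one misplaced case would be visible.

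**Working it through.** **Inputs.** Table 6-4 grades: microhemorrhages 1-4 Mild, 5-9 Moderate, 10 or more Severe; siderosis 1 area Moderate, 2 or more Severe; any macrohemorrhage Severe. Visit windows are from SAP Table 7-9, MRI timing and follow-up from Protocol 7.11.1.1 and 7.11.1.2, dosing rules from Protocol Table 7, and the safety cutoff from SAP 7.1.1.2.2.

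**1. Reproduce the SAP's own example.** SAP 6.3.7.2.2 works one case: "if there are 4 incident microhemorrhages, 1 incident areas of leptomeningeal hemosiderosis and no presence of macrohemorrhages on a BMW, ARIA-H is rated as"; the grade it gives is Moderate. Coding the table gives microhemorrhages Mild, siderosis Moderate, macrohemorrhage none, so the worst is Moderate. It agrees.

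**2. The two rules.** Let g(c, s) be the grade of component c on scan s, and G(s) the largest g(c, s) over the three components. The SAP picks a scan s* with the largest G and reports g(c, s*). A per-component rule reports the largest g(c, s) over all scans. The two agree only if s* is also the worst scan for every component.

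**3. Missed component.** Week 12: 5 microhemorrhages, no siderosis, so G = Moderate. Week 24: 5 microhemorrhages and 1 siderosis area, so G = Moderate. Both scans qualify as s*. Using Week 12, the overall row shows siderosis none; the per-component rule gives Moderate. The Week 24 by-visit row still shows the siderosis.

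**4. Under-graded component.** Scan 1: 2 microhemorrhages and 1 siderosis area (Moderate). Scan 2: 6 and 1 (Moderate). Using scan 1, microhemorrhage severity is Mild; the per-component rule gives Moderate.

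**5. When can this happen if findings persist?** If no component grade falls, the last scan is the worst for every component and always has the maximum G. Loss then requires a tie and the choice of an earlier scan. Counting grade patterns over two scans:
- Profiles: 4 × 3 × 2 = 24, less the all-none profile = 23.
- Persistent ordered pairs: (4·5/2) × (3·4/2) × (2·3/2) = 10 × 6 × 3 = 180, less 24 whose first scan is all-none = 156.
- Tied at Mild but different: 0. Tied at Moderate but different: 4.
- Tied at Severe but different: pairs whose first scan is below Severe number (4+3+2) × (3+2) × 2 = 90, so 180 − 90 = 90 start at Severe. Less the 18 identical pairs, this leaves 72.
- Total depending on the tie-break: 4 + 72 = 76 of 156. Certain loss: 0. No loss: 80.

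Without the persistence restriction there are 23 × 23 = 529 pairs: certain loss in 240, tie-dependent in 152, none in 137. These are counts of possible patterns, not expected frequencies.

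**6. What the dosing rules and cutoff remove.** Severe ARIA-H means permanent discontinuation, and safety data more than 90 days after the last dose are only listed. Suppose Severe ARIA-H is found on the MRI before the Week 13 dose. The last dose is then Day 57 and the cutoff is Day 57 + 90 = Day 147. The scheduled Week 24 scan falls 5-10 days before Day 169, on Days 159-164, so it is outside every summary table under either rule. Many Severe ties therefore never arise in the tables. The Moderate example in step 3 needs dosing to resume after Week 12, so that the Week 24 scan is inside the cutoff.

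**7. What remains.** New ARIA-H requires follow-up MRI every 4-6 weeks. After a scan on Days 75-80 (5-10 days before Day 85), the next falls between Day 75 + 28 = 103 and Day 80 + 42 = 122. That is before Day 147 and inside the Week 12 window of Days 72-127. Several scans in one window are thus built into the schedule, and the by-visit row can be affected too.

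**The case against.** The strongest reply is that little is lost. With persistent findings there is no loss if the latest tied scan is used, and the announced worst-case approach hardly suggests choosing the less affected scan. By-visit rows show a component in whichever later summarised window it appears. The AESI tables by preferred term and the full MRI listing stand regardless. All of this is right about size, but it does not supply the missing rule: the worst-case text governs presence and overall severity, not the choice between tied scans.

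Three stronger readings are tempting and not supported.
- A reader might infer that a participant who is Severe at Week 12 and later gains siderosis and a macrohemorrhage would routinely have both dropped by this rule. Permanent discontinuation and the 90-day cutoff put most such scheduled scans outside the tables under any selection rule.
- A reader might infer loss without a tie, for example 10 microhemorrhages and no siderosis chosen over 9 and 1. That needs a finding to shrink or disappear, which Protocol 7.11 describes as very rare.
- A reader might fault the first-occurrence table for omitting later components. It is defined and labelled as describing the first ARIA-H, so that is its purpose.

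**Conclusion.** The point holds for the any-occurrence table. As written, component severity in the overall row, and in any visit window with several scans, can be missing or too low when scans tie on overall ARIA-H grade, and the SAP leaves the outcome to an unstated programming choice. This rests on reading the selected ARIA-H as one scan, as SAP 6.3.7.2.1 defines the event, and on findings mostly persisting.

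The effect is limited. Under persistence it arises only through ties, and the Severe ties are thinned by discontinuation and the cutoff. A reader might want a percentage of siderosis or macrohemorrhage cases lost, but the documents give no per-scan component rates, so any such figure would reflect the rates assumed. Overall ARIA-H incidence, its maximum severity, the AESI tables and the listings do not change. It merits correction because the replacement is clearly better and nearly free, and the tables concern an identified risk.

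**What to change.** In SAP 7.5.7, replace the sentence on component severity for any occurrence with a rule of this kind: for each participant, the maximum severity of microhemorrhages, of leptomeningeal hemosiderosis and of macrohemorrhages is taken separately over all summarised scans, within each visit window and overall post-baseline, regardless of which scan is selected for overall ARIA-H severity. No tie-break is then needed. Leave the first-occurrence table as defined.

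The cost is one SAP sentence and a small programming change, with no new data. Component rates may look slightly less favourable.

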# 7.5.8 Ophthalmological Examinations

Incidence of any post-baseline treatment-emergent PCS ophthalmological examinations findings as indicated on the Optical Coherence Tomography, Visual Acuity, Slit Lamp Exam, and Fundoscopy electronic CRFs will be summarized for each visit (refer to Table 7-10 for analysis visit window definition), and overall during the treatment period. For overall, the record with the most severe finding will be selected for a participant. PCS ophthalmological examinations findings are defined as:

- On the Optical Coherence Tomography electronic CRF
  - $\circ$  Percent CFB in left eye retinal central subfield thickness (in micrometers)  $\geq 20\%$ ,
  - o Percent CFB in right eye retinal central subfield thickness (in micrometers)  $\geq 20\%$ ,
  - o Percent CFB in left eye subfoveal choroidal thickness (in micrometers) > 20%,
  - o Percent CFB in right eye subfoveal choroidal thickness (in micrometers)  $\geq 20\%$ .
- On the Visual Acuity electronic CRF
  - Left eye best-corrected visual acuity worsens 3 categories since baseline (the higher the best-corrected visual acuity, the worse):
    - 20/32 and 20/30 are pooled and are considered one category,
    - When counting, 3 categories do not include the baseline assessment but include the post-baseline assessment, e.g., from 20/20 at baseline to 20/40 at a post-baseline, it is counted as worsening 3 categories.
  - o Right eye best-corrected visual acuity worsens 3 categories since baseline.
- On the Slit Lamp Exam electronic CRF
  - o Left Anterior Cell Score by SUN Criteria ≥ 0.5 (the higher the Anterior Cell Score, the worse),
  - o Right Anterior Cell Score by SUN Criteria  $\geq 0.5$ .
- On the Fundoscopy electronic CRF
  - o Left eye results shown as abnormal (clinically significant),
  - o Right eye results shown as abnormal (clinically significant),
  - o Left eye results shown as abnormal (not clinically significant),
  - o Right eye results shown as abnormal (not clinically significant).

All ophthalmological examinations findings will be listed separately by electronic CRF.

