1.3. Summary of Risks and Benefits

Based on preclinical observations and evidence reported in the literature, the proposed mechanism of action of AL002 (ie, agonism of TREM2) has the potential to alter the course of AD progression. Due to a paucity of therapeutic options for prevention, slowing, or cure for AD, a safe and effective therapy that targets TREM2 without blocking the ability of natural ligands to

Alector, Inc.

induce an additive or synergistic effect may provide a favorable risk/benefit profile to participants with this condition.

Preclinical toxicology studies evaluating AL002 with long-term, dose-intensive regimens has identified ocular toxicity as a potential risk for AL002. Cynomolgus monkeys treated with 80 mg/kg or 250 mg/kg weekly for 27 doses had postmortem microscopic findings of inflammation in the ciliary body and choroid of the eye with no corresponding ophthalmic findings or associated clinical observations (for additional information, please see Section 4.3 of the IB). Because of these findings, uveitis has been added as a potential risk to treatment with AL002, and all treated participants will be monitored by an eye specialist (see Section 6.5.3 of the IB and Section 6.5.7 in this protocol). In the Phase 1 study (Study AL002-1), eye-related AEs have been limited to mild and transient events.

Amyloid-related imaging abnormalities-edema (ARIA-E) and amyloid-related imaging abnormalities-hemosiderin deposits (ARIA-H) have been observed in Study AL002-2. These data are described in the IB, including any issued addenda. Additional magnetic resonance imaging (MRI) monitoring has been added to this protocol and the Dosing Guidelines for ARIA have been updated (Section 7.11 and Schedules of Assessments [Section 14.1]). Because serious and severe symptomatic cases occurred in participants with an *APOE* e4/e4 genotype, participants with this genotype may no longer be enrolled into this trial. All currently enrolled participants with an *APOE* e4/e4 genotype will no longer receive study drug, but should continue with all study visits and assessments.

For this Phase 2 study, AL002 is to be administered for up to 96 weeks via IV infusion and is expected to be generally safe and well tolerated. To further mitigate potential risks associated with dosing, enrolled participants randomized to 40 or 60 mg/kg will be titrated to their assigned dose over 2 or 3 doses, respectively.

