- 9. Participant has any of the following eye conditions: a history or presence of uveitis, a serious chronic inflammatory condition of the eye, a current eye infection, or any ongoing eye disorder requiring anticipated invasive eye procedures or injectable medical therapy (eg, ranibizumab or aflibercept for macular degeneration or diabetic eye disease) during the study period.
- 10. Participant has any history of schizophrenia, schizoaffective disorder, major depression, or bipolar disorder.
 - a. A history of major depression is acceptable if no episode has been reported within the previous 2 years. Treatment with antidepressant medications is allowed.
- 11. Participant is at risk of suicide in the Investigator's opinion.

Alector, Inc.

- 12. Participant has history of alcohol and/or moderate to severe substance use disorder (according to the Diagnostic and Statistical Manual of Mental Disorders, 5th Edition) within the past 2 years.
 - a. Nicotine use is allowed.

Imaging-related exclusion criteria:

- 13. Participant has MRI evidence of
 - a. >2 lacunar infarcts.
 - b. Any territorial infarct > 1 cm³.
 - c. White matter hyperintense lesions on the FLAIR sequence that correspond to an overall Fazekas score of 3.
- 14. Participant has presence on MRI of >5 microbleeds and/or >1 area of leptomeningeal hemosiderosis based on central read.
- 15. Participant has presence of significant cerebral vascular pathology as assessed by the MRI Central Reader.
- 16. Participant is unable to tolerate MRI procedures (eg, due to anxiety or claustrophobia) or has contraindication to MRI, including but not limited to, the presence of pacemakers that are not MRI compatible, aneurysm clips, artificial heart valves, ear implants, or foreign metal objects in the eyes, skin, or body that would contraindicate an MRI scan; or any other clinical history or examination finding that would pose a potential hazard in combination with MRI. Those who are able to tolerate MRI with intermittent use of a low-dose benzodiazepine or anxiolytic are permitted and may be included in the study.

Cardiovascular disorders-related exclusion criteria:

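### SAP 7.5.8 counts fundus results graded not clinically significant as treatment-emergent PCS findings, and sets no baseline condition for fundoscopy or the anterior chamber cell score

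*SAP*

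**What the plan says.** SAP 7.5.8 plans a descriptive table of "Incidence of any post-baseline treatment-emergent PCS ophthalmological examinations findings", by visit and overall, with the most severe record used for the overall entry. The PCS criteria are listed by examination:

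- **OCT:** percent change from baseline of at least 20% in retinal or choroidal thickness, per eye.
- **Visual acuity:** "Left eye best-corrected visual acuity worsens 3 categories since baseline", and the same for the right eye.
- **Slit lamp:** "Right Anterior Cell Score by SUN Criteria" of 0.5 or more, and the same for the left eye. No baseline condition is given.
- **Fundoscopy:** "Left eye results shown as abnormal (clinically significant" and, as a separate item, "Left eye results shown as abnormal (not clinically significant", each repeated for the right eye. No baseline condition is given.

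All findings are also listed. No ophthalmology shift table is planned.

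Protocol 1.3 explains why the eyes are examined: "uveitis has been added as a potential risk to treatment with AL002, and all treated participants will be monitored by an eye specialist".

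**The concern.** There are two separate problems in one definition. First, a result that the examiner graded as not clinically significant is tabulated as potentially clinically significant. Because the other abnormal grade is listed too, any abnormal fundus result meets the fundoscopy criteria. Second, the heading says treatment-emergent, but two of the four examinations have no comparison with baseline and the term is not defined for eye findings. Two programmers could follow this section faithfully and produce different tables.

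Under the literal reading, someone with an unchanged fundus abnormality since screening would count as a treatment-emergent case at each examination, whichever arm they are in. That raises the rate in all arms, including placebo, and shrinks the relative contrast in any row that pools abnormal fundus results or any PCS finding. The safety endpoint in Protocol Section 2 and SAP Table 2-1 is change from baseline in ophthalmological findings, and a count without a baseline comparison does not measure that.

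**Working it through.** **1. Is a baseline comparison stated?**

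| Item | Baseline comparison stated |
|---|---|
| OCT thickness (SAP 7.5.8) | Yes, percent change |
| Visual acuity (SAP 7.5.8) | Yes, categories worsened |
| Anterior cell score (SAP 7.5.8) | No |
| Fundoscopy, both abnormal grades (SAP 7.5.8) | No |
| Neurological examination (SAP 7.5.9) | Shift tables from baseline |
| Vital signs (SAP 7.5.6) | Yes |

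**2. Does treatment-emergent supply the missing condition?** The documents use the term in different ways. For vital signs, "A post-baseline vital signs value is considered treatment-emergent potentially clinically significant (PCS) if it meets both the observed value and the CFB criteria". For adverse events, SAP 6.3.2.1 uses timing alone, while Protocol 7.1 requires an event absent before exposure or worse than at baseline. SAP 6.3 names the eye variable as a change from baseline. None of these is applied to the fundoscopy or slit-lamp items, so the term is open.

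**3. Can participants enter with a stable fundus abnormality?** Exclusion criterion 9 removes uveitis, serious chronic inflammation, current infection and "any ongoing eye disorder requiring anticipated invasive eye procedures or injectable medical therapy". Other stable fundus conditions are not excluded, and the age range is 50 to 85. A raised cell score at entry should be uncommon, because uveitis and infection are excluded, so the practical effect lies mainly in fundoscopy.

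**4. Denominators.** The plan's sample size reproduces: 4 × 70 + 15 + 6 + 27 = 328, and 328 / 4 = 82 per group (Protocol 8.1, SAP 3.5). Safety tables are primarily for dosed participants who are not e4/e4. Taking the 15 as e4/e4 and dosed, and the 6 as never dosed, gives (328 − 15 − 6) / 4 = 76.75, or about 77 per arm.

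**5. Illustration of dilution.** All rates here are assumptions. Let *b* be the proportion with a stable fundus abnormality at baseline, and *r* the rate of new findings: 1% on placebo, 11% on one dose. If stable abnormalities count, the rate in a pooled row is

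p = b + (1 − b) × r.

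For b = 0.10: placebo 0.10 + 0.90 × 0.01 = 10.9%; drug 0.10 + 0.90 × 0.11 = 19.9%; ratio 19.9 / 10.9 = 1.8.

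The last column shows how hard the difference would be to see. It is the normal-approximation power of a two-sided 5% comparison with 77 per arm, Φ[(d − 1.96 × SE₀) / SE₁], where d is the difference in rates, SE₀ uses the pooled rate and SE₁ the separate rates. For b = 0: d = 0.10, SE₀ = √(0.06 × 0.94 × 2/77) = 0.0383, SE₁ = √((0.0099 + 0.0979)/77) = 0.0374, so Φ(0.67) = 75%. An exact Fisher calculation gives 68% for the same row.

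| b (assumed) | Placebo | Drug | Ratio | Power |
|---|---|---|---|---|
| 0% (new findings only) | 1.0% | 11.0% | 11 | 75% |
| 10% | 10.9% | 19.9% | 1.8 | 34% |
| 20% | 20.8% | 28.8% | 1.4 | 21% |
| 30% | 30.7% | 37.7% | 1.2 | 15% |
| 50% | 50.5% | 55.5% | 1.1 | 9% |

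The SAP plans no such test. The power column only describes how visible a difference would be to a reader of the table.

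**The case against.** The strongest reply is that the table is already limited to treatment-emergent findings and the bullets define only PCS, so a baseline filter is implied. The change-from-baseline endpoint and the Protocol 7.1 definition support that reading. This has force: it cannot be said that stable disease will certainly be counted. But SAP 6.3.2.1 shows that the same SAP can use the term for timing alone, and OCT and visual acuity carry their own baseline clause where fundoscopy does not. The ambiguity stands.

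A reader might infer that the definition breaks an SAP-wide treatment-emergent rule. It does not. The rule in 7.5.6 covers vital signs only, and 7.5.9 uses the same term for neurology with no threshold at all.

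A reader might also infer that a uveitis signal could be hidden. The documents do not support that. Uveitis of Grade 2 or higher is an AESI with its own summaries and listing. Protocol 6.5.7 requires signs and symptoms of uveitis to be recorded as AEs and followed. The cell score, OCT thickness and the clinically significant fundus grade are separate items, and the iDMC reviews safety data unblinded. If the fundus items are reported as separate rows, the lower grade cannot dilute the higher one. A stable, clinically significant abnormality present at baseline would still count in its own row, however.

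Finally, Protocol 8.3.4 plans incidences of ophthalmological abnormalities without limiting them to significant ones, and the monkey lesions had no ophthalmic findings in life. Both argue for keeping low-grade changes visible. That is right, and it is a reason for a shift table. It does not justify a PCS label.

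**Conclusion.** The point holds as a defect in a descriptive safety table. The label contradicts the grade it includes, and the fundoscopy and cell-score criteria lack the baseline condition that the neighbouring items have. On the literal reading, pre-existing fundus abnormality inflates every arm and dilutes pooled rows. Its size is unknown: the illustration takes an 11-fold contrast down to between 1.8-fold and 1.1-fold for a background of 10% to 50%, but it rests on assumed event rates, an assumed prevalence, pooled grades and no baseline filter. The efficacy analyses and the AE and AESI tables are unaffected. It is worth correcting before the tables are programmed, because the eyes are examined for a named potential risk and the correction is small.

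**What to change.** In SAP 7.5.8:

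1. Define treatment-emergent for fundoscopy and the anterior chamber cell score as new or worsened relative to that eye's own baseline.
2. Report the abnormal, not clinically significant fundus grade outside the PCS count.
3. Add a per-eye table of shifts from baseline to worst post-baseline grade (normal; abnormal, not clinically significant; abnormal, clinically significant), by arm, in line with the shift tables in SAP 7.5.9.

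The screening eye examinations needed for this are already scheduled, so no new data are required. The cost is SAP wording and one more table. The downside is that new low-grade fundus changes leave the PCS count, but they stay visible by arm in the shift table. If dilution figures are quoted when this is discussed, label them as illustrations with assumed rates.
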